12.8. Causality Assessment

The investigator's assessment of causality must be provided for all adverse events (serious and non-serious), the investigator must record the causal relationship in the CRF, as appropriate, and report such an assessment in accordance with the serious adverse reporting requirements if applicable. An investigator's causality assessment is the determination of whether there exists a reasonable possibility that Axitinib caused or contributed to an adverse event. If the investigator does not know whether or not Axitinib caused the event, then the event will be handled as "related to investigational product" for reporting purposes, as defined by Pfizer, Inc. (See Section on Reporting Requirements). If the investigator's causality assessment is "unknown but not related to investigational product," this should be clearly documented on trial records.

In addition, if the investigator determines a serious adverse event is associated with trial procedures, the investigator must record this causal relationship in the source documents and CRF, as appropriate, and report such an assessment in accordance with the serious adverse event reporting requirements, if applicable.

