12.2. Reporting Period

Adverse events reporting, including suspected, unexpected serious adverse reactions, will be carried out in accordance with applicable local regulations. For serious adverse events, the reporting period to Pfizer, Inc. or its designated representative begins from the time that the subject has taken at least one dose of trial treatment through the last subject visit. Any serious adverse event occurring any time after the reporting period must be promptly reported if a causal relationship to Axitinib is suspected.

Adverse events should be recorded on the CRF from the time the subject has taken at least one dose of trial treatment through last subject visit.

If a patient begins a new anticancer therapy, the adverse event reporting period for non-serious adverse events ends at the time the new treatment is started. Death must be reported if it occurs

during the serious adverse event reporting period after the last dose of investigational product, irrespective of any intervening treatment.

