14.2. Safety Analysis

All patients receiving at least 1 dose of Axitinib under this protocol will be included in the safety analyses. Adverse events will be coded and grouped by body system. The incidence of each adverse event will be tabulated and displayed by starting dose level. Tabulations by maximum severity and relationship to Axitinib will also be included. Summary patient listings will be provided for SAEs, adverse events resulting in discontinuation of Axitinib, and deaths within 28 days of drug discontinuation and possibly or probably related to Axitinib.

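### The 14.2 death listing can omit early deaths judged unrelated to axitinib and uses relatedness terms that 12.8 does not define; a few deaths could miss both safety listings

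*Combined protocol and SAP*

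**What the plan says.** Section 14.2 (Safety Analysis) covers everyone who received at least one dose. It states: "Summary patient listings will be provided for SAEs, adverse events resulting in discontinuation of Axitinib", and then, as the third listing, "deaths within 28 days of drug discontinuation and possibly or probably related to Axitinib". It also says "Tabulations by maximum severity and relationship to Axitinib will also be included", without naming the relationship categories.

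Section 12.8 (Causality Assessment) defines the judgement as the "determination of whether there exists a reasonable possibility that Axitinib caused or contributed to an adverse event". When the investigator cannot say, the rule is: "If the investigator does not know whether or not Axitinib caused the event, then the event will be handled as" related to the product, for reporting purposes. A separate outcome, "unknown but not related to investigational product", need only be documented. On recording, "the investigator must record the causal relationship in the CRF, as appropriate".

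Section 12.2 (Reporting Period) says that the SAE reporting period "begins from the time that the subject has taken at least one dose of trial treatment through the last subject visit". A later SAE must be reported if a causal link to axitinib is suspected. Section 12.5 makes any event resulting in death an SAE and has a fatal malignancy in the study or safety period recorded as a grade 5 SAE. Section 7.1 provides 28 days of safety follow-up after study participation ends.

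**The concern.** The trial is open label with one arm, so the relatedness of an early death is judged by an unblinded investigator with no control rate to check it against. A death listing filtered on that judgement can be short or empty while deaths shortly after stopping are not rare. Section 11 asks for special attention to hypertension, thrombosis, hemoptysis and bleeding, and a death attributed to the cancer could still involve one of these. A reader would want to see each such death and the attribution together.

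The second problem is vocabulary. The listing selects on possible or probable relationship, while 12.8 defines no such grades. Someone must decide how a 12.8 outcome, including an unknown relationship, enters the listing. As written, that decision would be made after the deaths are known.

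**Working it through.** No stated figure depends on this point, so the main check is textual: which deaths appear where, with the 14.2 death item read as a conjunction. All rows concern deaths within 28 days of stopping axitinib.

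| Death | Death listing (14.2) | SAE listing (14.2, 12.5, 12.2) | OS analysis (14.1) |
|---|---|---|---|
| By last visit, judged related | Listed | Listed | Counted |
| By last visit, relationship unknown | Not specified | Listed | Counted |
| By last visit, judged unrelated | Not listed | Listed | Counted |
| After last visit, judged related | Listed | Reportable | Counted |
| After last visit, relationship unknown | Not specified | Reportable if the 12.8 default is applied | Counted |
| After last visit, judged unrelated | Not listed | Not required | Counted |

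Two things follow.

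1. In the third row the death listing loses a death, but the SAE listing still shows it.
2. Only the last row misses both safety listings. That row can be occupied because the Table 6 schedule shows no end-of-treatment or 28-day visit, and later survival contact is every three months, give or take one month, and may be by telephone (Table 6 notes, Section 18). A patient who stops and dies before returning may therefore have had the last visit already.

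The OS analysis counts that death, but from treatment start and without attribution, so it does not identify it as a death soon after stopping.

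**Scale of the window.** Inputs: six-month survival S6 of 0.70 (target) or 0.50 (historical) and n = 37, from Section 13. Assumptions: constant hazard, 30.44 days per month, and all 37 patients entering the window.

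- Hazard per month: h = −ln(S6)/6, which is 0.0594 for S6 = 0.70 and 0.1155 for S6 = 0.50.
- P(death in 28 days) = 1 − exp(−h × 28/30.44), which is 0.053 and 0.101.
- Expected deaths: 37 × 0.053 = 2.0 and 37 × 0.101 = 3.7.

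These are deaths from any cause in a 28-day window. They are not an estimate of deaths omitted, which would also need the share judged unrelated and the share occurring after the last visit. The documents give neither.

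**The case against.** The strongest reply is that little or nothing is lost, for five reasons.

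- **The wording is ambiguous.** The 14.2 item can also mean deaths within 28 days, plus deaths possibly or probably related. On that reading every death in the window is listed. This stands as an alternative, but the conjunction is the plainer grammar, and the two readings give different listings.
- **The terms may map.** A reasonable possibility translates naturally to possibly related, and Section 12.9 uses that phrase for an investigator's attribution. The CRF is not among the documents, so a graded field cannot be ruled out. This stands, and it limits the point to terms that 12.8 leaves undefined.
- **Deaths are listed as SAEs.** That holds for deaths in the reporting period, whatever their attribution. After it, 12.2 still requires a report when causality is suspected, and the 12.8 default would bring in unknown relationships. It does not reach later deaths judged unrelated.
- **The gap may be empty.** Section 12.2 does not say where the last visit falls relative to day 28, and 7.1 promises 28 days of safety monitoring. This stands: the gap is possible, not demonstrated.
- **All-cause mortality cannot be hidden.** Death from any cause is the primary endpoint, one dose makes a patient evaluable (13.1, 14.1), and OS rates at 2, 4 and 6 months are reported (13.4). This stands in full.

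A reader might go further and infer that deaths of unknown relationship necessarily drop out of the listing. The documents do not support that: nothing excludes them from possibly related, and because the 12.8 default is stated for reporting, its use in analysis is undefined rather than contradicted. Nor does the default cover every unknown, since 12.8 keeps unknown-but-not-related apart.

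**Conclusion.** The point holds in a limited form. On its plain reading, 14.2 leaves early deaths judged unrelated off the death listing and selects on terms that 12.8 does not define. The SAE listing and the OS analysis cover most of these deaths. The residual gap is a death judged unrelated, after the last subject visit and within 28 days of the last dose. Its size cannot be computed from the documents. The 2.0 to 3.7 of 37 only illustrates all-cause deaths in such a window and rests on the assumptions stated with the calculation.

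Two further inferences are tempting and should not be drawn. One is that a death clearly caused by axitinib would go unlisted. That requires a definite grade, which 12.8 does not have either. The other is that the toxicity objective (3.2, item 5) would be answered too favourably. That objective is served mainly by the proportion with grade 3 or worse toxicity and the toxicity tabulations (13.4, 14.2), so the death listing does not decide it.

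This is a worthwhile, inexpensive improvement to safety reporting. It does not affect the primary analysis.

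**What to change.** - **Section 14.2, death listing.** List all deaths from first dose to 28 days after the last dose, regardless of cause or attribution. Show the 12.8 outcome as a column with three values: related; unknown, handled as related; not related (including unknown but not related). Report the number and proportion of treated patients with an exact 95% CI. Starting at first dose also settles deaths on treatment, which the present wording does not clearly place.
- **Section 14.2, relationship tabulation.** Use the same three categories, so that the handling of an unknown relationship is fixed before the data are seen.
- **Section 12.2.** Align the reporting period so that every death in the 28-day safety follow-up of 7.1 is recorded with an attribution, and state that these 28 days and those in 14.2 start from the same date. Without this, the new column could be blank for the deaths it is meant to show.

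The cost is wording in two sections and an attribution for a few more deaths. Death dates are already needed for the primary endpoint. The downside is that the listing may look less favourable, since it will include deaths that the investigator attributes to the cancer; the attribution column shows which these are.

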12.9. Exposure In Utero

An Exposure In Utero (EIU) occurs if:

1. A female becomes, or is found to be, pregnant either while receiving or having been directly exposed to (e.g., environmental exposure) Axitinib, or the female becomes, or is found to be, pregnant after discontinuing and/or being directly exposed to Axitinib (maternal exposure);

2. A male has been exposed, either due to treatment or environmental, to Axitinib prior to or around the time of conception and/or is exposed during the partner pregnancy (paternal exposure).

If any study subject or study subject's partner becomes or is found to be pregnant during the study subject's treatment with Axitinib, the investigator must submit this information to Pfizer, Inc. on an Exposure in Utero Form. In addition, the investigator must submit information regarding environmental exposure to Pfizer, Inc. product in a pregnant woman (e.g., a nurse reports that she is pregnant and has been exposed to a cytotoxic product by inhalation or spillage) using the Exposure in Utero Form. This must be done irrespective of whether an adverse event has occurred and within 24 hours of awareness of the pregnancy. The information submitted should include the anticipated date of delivery (see below for information related to induced termination of pregnancy).

Follow-Up is conducted to obtain pregnancy outcome information on all Exposure in Utero reports with an unknown outcome. The investigator will follow the pregnancy until completion or until pregnancy termination (ie, induced abortion) and then notify Pfizer, Inc. of the outcome. The investigator will provide this information as a follow up to the initial Exposure in Utero Form. The reason(s) for an induced abortion should be specified. An EIU report is not created when an ectopic pregnancy report is received since this pregnancy is not usually viable. Rather, a serious adverse event case is created with the event of ectopic pregnancy.

If the outcome of the pregnancy meets the criteria for immediate classification as a serious adverse event (ie, spontaneous abortion, stillbirth, neonatal death, or congenital anomaly [including that in an aborted fetus, stillbirth or neonatal death]), the investigator should follow the procedures for reporting serious adverse events.

In the case of a live birth, the "normality" of the newborn can be assessed at the time of birth (ie, no minimum follow-up period of a presumably normal infant is required before an Exposure in Utero Form can be completed). The "normality" of an aborted fetus can be assessed by gross visual inspection, unless pre-abortion test findings are suggestive of a congenital anomaly.

Additional information about pregnancy outcomes that are classified as serious adverse events follows:

- "Spontaneous abortion" includes miscarriage and missed abortion.

- All neonatal deaths that occur within 1 month of birth should be reported, without regard to causality, as serious adverse events. In addition, any infant death after 1 month that the investigator assesses as possibly related to the in utero exposure to Axitinib should be reported.

Additional information regarding the Exposure in Utero may be requested by the investigator. Further follow-up of birth outcomes will be handled on a case-by-case basis (e.g., follow-up on preterm infants to identify developmental delays). In the case of paternal exposure, the investigator must obtain permission from the subject's partner in order to conduct any follow-up or collect any information.

12.10. Withdrawal Due to Adverse Events

Withdrawal due to adverse event should be distinguished from withdrawal due to insufficient response, according to the definition of adverse event noted earlier, and recorded on the appropriate adverse event CRF page.

When a subject withdraws due to a serious adverse event, the serious adverse event must be reported in accordance with the reporting requirements defined below.

12.11. Eliciting Adverse Event Information

The investigator is to report all directly observed adverse events and all adverse events spontaneously reported by the trial subject. In addition, each trial subject will be questioned about adverse events.

12.12. Reporting Requirements

Each adverse event is to be assessed to determine if it meets the criteria for serious adverse event. If a serious adverse event occurs, it will be reported via submission of Pfizer, Inc. Investigator-Initiated Research Serious Adverse Event (IIR SAE) form, according to guidelines provided in Pfizer, Inc. IIR Safety Reporting Reference Manual Version 3, and IIR SAE Form Completion Guide, or Form FDA 3500 A (Med Watch Form) . This will be faxed to Pfizer, Inc. U.S. Clinical Trial Department at [name] using the Pfizer, Inc. Investigator Initiated Research Reportable Event Fax Cover Sheet. The Investigator-Initiated Research Serious Adverse Event (IIR SAE) form must be submitted to Pfizer, Inc. immediately for a death or life-threatening event, and within 24 hours for all other types of SAEs. Any SAEs reported to Pfizer, Inc. should also be faxed to NCCN at [contact] or emailed via [contact].

All Serious adverse Events (SAE's) will have written report sent to:

- 1. Principal Investigator of the study: [contact]
- 2. Data Manager

3. The Oncology Clinical Trials Support Unit (O-CTSU) staff will coordinate the reporting process between the Investigator and the IRBMED as well as other applicable reporting agencies (FDA, CTEP, NCCN, Pfizer, Inc.). Copies of all related correspondence and reporting documents will be maintained in the regulatory file.

Deaths or life-threatening adverse events will be reported to the University of Michigan Medical Institutional Review Board (IRBMED) in accordance with the reporting policy of the IRB.

12.12.1. Serious Adverse Event Reporting Requirements

If a serious adverse event occurs, NCCN and Pfizer, Inc. are to be notified within 24 hours of awareness of the event by the investigator. In particular, if the serious adverse event is fatal or life-threatening, notification to Pfizer, Inc. must be made immediately, irrespective of the extent of available adverse event information. This timeframe also applies to additional new information (follow-up) on previously forwarded serious adverse event reports as well as to the initial and follow-up reporting of Exposure in Utero cases. Pfizer, Inc. and NCCN should be notified via the reporting requirements stipulated in Section 12.12 (Reporting Requirements). Such events will be reported via submission of Pfizer, Inc. Investigator-Initiated Research Serious Adverse Event (IIR SAE) form, according to guidelines provided in Pfizer, Inc. IIR Safety Reporting Reference Manual Version 3, and IIR SAE Form Completion Guide, or Form FDA 3500 A (Med Watch Form). This will be faxed to Pfizer, Inc. U.S. Clinical Trial Department at [name] using the Pfizer, Inc. Investigator Initiated Research Reportable Event Fax Cover Sheet. The Investigator-Initiated Research Serious Adverse Event (IIR SAE) form must be submitted to Pfizer, Inc. immediately for a death or life-threatening event, and within 24 hours for all other types of SAEs. Any SAEs reported to Pfizer, Inc. should also be faxed to NCCN at [contact] or emailed via [contact].

In the rare event that the investigator does not become aware of the occurrence of a serious adverse event immediately (e.g., if an outpatient study subject initially seeks treatment elsewhere), the investigator is to report the event within 24 hours after learning of it and document the time of his/her first awareness of the adverse event.

For all serious adverse events, the investigator is obligated to pursue and provide information to NCCN and Pfizer, Inc. in accordance with the timeframes for reporting specified above. In addition, an investigator may be requested by Pfizer, Inc. to obtain specific additional follow-up information in an expedited fashion. This information may be more detailed than that captured on the adverse event case report form. In general, this will include a description of the adverse event in sufficient detail to allow for a complete medical assessment of the case and independent determination of possible causality. Information on other possible causes of the event, such as concomitant medications and illnesses must be provided. In the case of a subject death, a summary of available autopsy findings must be submitted as soon as possible to Pfizer, Inc. or its designated representative.

12.12.2. Non-Serious Adverse Event Reporting Requirements

Non-serious adverse events are to be reported on the adverse event CRFs, which are to be submitted to Pfizer, Inc..

12.13. Data and Safety Monitoring

12.13.1 This study will be monitored in accordance with the NCI approved University of Michigan Rogel Cancer Center Data and Safety Monitoring Plan.

12.13.2. The study team will meet quarterly or more frequently depending on the activity of the protocol. During these regular meetings, the study team will discuss matters related to:

- 1. safety of study participants (SAE/UaP reporting)
- 2. validity and integrity of the data
- 3. enrollment rate relative to expectations, characteristics of participants
- 4. retention of participants, adherence to protocol (potential or real protocol deviations)
- 5. data completeness

12.13.3. Study team meetings will be documented by the Protocol Specific Data and Safety Monitoring Report (DSMR). The data manager or designee assigned to the trial will be responsible for completing the report. DSMRs will be signed by the Principal Investigator or by one of the co-investigators and will be kept on file in the Oncology Clinical Trials Support Unit (O-CTSU).

12.13.4. The University of Michigan Rogel Cancer Center Data and Safety Monitoring Committee (DSMC) will provide independent oversight of the safety and data integrity for this trial. DSMRs and any other pertinent documents will be submitted to the DSMC for review on a quarterly basis unless specified more frequently by a DSMC ruling.

12.13.5. The Principal Investigator or designee will forward all correspondence and recommendations generated by the DSMC to the Institutional Review Board.

13. STATISTICAL METHODS

13.1. Primary Objectives:

The primary aim of this study is to compare 6-month overall survival after treatment with Axitinib in patients with unresectable, recurrent or metastatic head and neck cancer to historical rates. Based on results in the literature, we assume a 6-month mortality rate of **50%** under current standard care in this patient population (11, 52). We will test whether survival after treatment with Axitinib is improved to 70% at 6-months compared to 50%.

Overall survival will be determined from the date of treatment initiation to date of death from any cause. For the primary endpoint, patients that are alive at 6 months following the initiation of study treatment will be considered successful. All other patients will be considered unsuccessful. Patients will be considered evaluable for the primary endpoint if they receive any dose of Axitinib.

13.2. Sample size justification:

We will enroll 37 additional patients for comparison of overall survival. Based on historical data, 6 month OS in heavily pretreated patients such as those included in this study is 50%. Thirtyseven patients will provide 80% power to detect a meaningful difference in proportion alive at 6months (70% vs 50% historically) with a type I error rate of 5%. For the primary endpoint of overall survival we anticipate no missing data and will test whether the proportion alive at 6 months is greater than the historical rate of 50% with an upper tailed test of binomial proportion.

Based on our prior experience at the University of Michigan, we anticipate accrual of approximately 4 patients every 5 months. With this rate of accrual, we can enroll 40 eligible patients in 50 months. With a minimum follow-up of 6 month for each patient, the study will complete in about 56 months.

13.3. Stopping rules for futility:

As we observed considerable evidence of activity in UMCC 2011.053, we plan no interim analysis for futility with data collected in the expansion cohort B. Formal analysis of efficacy will be performed at trial completion.

13.4. Analysis plan:

- To estimate survival rates.

Overall and progression-free survival rates at 2, 4 and 6 months will be reported along with 95% confidence intervals based on the binomial distribution. Kaplan-Meier methods will also be conducted to estimate these rates and the medians of PFS and overall survival (OS) of the 37 evaluable patients, with a corresponding standard error estimate based on Greenwood's formula (53).

Among this cohort of patients, progression will be determined based on Choi critieria.

- To determine the response.

The best overall response rate will be determined for each evaluable patient at 8 and 16 weeks following the start of Axitinib. The proportion of evaluable patients who have an objective response (complete or partial) and stable disease will be calculated, and a 95% exact binomial confidence interval will be determined.

- To determine the toxicity profile of this treatment regimen.

The proportion of treated patients experiencing any clinically significant (Grade 3 or worse) toxicity will be determined, with a 95% exact binomial confidence interval; specific toxicities of all grades will be tabulated.

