1.2. Rationale for Trial

Based off the known translational data and targeted mechanism of Axitinib, UMCC 2011.53 'A Phase II Trial Evaluating Axitinib in Patients with Unresectable, Recurrent, or Metastatic Head and Neck Cancer' accrued patients between 2012-2014. This study included patients with unresectable recurrent or distant metastatic (R/M HNSCC) at any line of therapy as long as their ECOG performance status was 0-2. It was powered with the primary objective of detecting an improvement in 6-month progression free survival. Of particular note, tumor response was judged by RECIST v1.0 with planned treatment cessation if radiologic progression was noted.

Forty-two patients were enrolled and available for safety analysis of which only 30 were available for efficacy. We noted that many patients in this cohort had significant clinical improvement as witnessed by symptomatic improvement, improved energy, and increased performance status. However, interval imaging of patients demonstrated evidence of mild/moderate tumor swelling with cystic attenuation and edema suggestive of drug effect. In some of the patients, this likely treatment response was interpreted as progression per RECIST v1.0. Planned interim analyses were conducted as to investigate efficacy as based on 6 month progression free survival (PFS). The first a priori interim analysis was performed after enrollment of 20 patients and marginal benefit was seen hence a second interim analysis was performed after enrollment of 30 patients evaluable for efficacy. Using the endpoint of 6 month PFS, the study was stopped due to futility as the observed rate for patients on axitinib was 27%.

Final results of this trial were recently published (55). Although the trial was considered negative on grounds of lack in improvement of PFS compared to historical controls (3.7 months (95% CI 3.5-5.7), observed responses and survival data suggested significant efficacy in a heavily pre-treated population (disease control rate (DCR) of 76.7%, median OS of 10.9 months (95% CI 6.4-17.8)) (Table 8, Figure 3, Figure 4). In addition, Axitinib was extremely well tolerated with no bleeding episodes or reductions due to home blood pressure readings.

Response	RECIST v1.0	Choi Criteria
Complete Response	0 (0%)	0 (0%)
Partial Response	2 (6.7%)	19 (65%)
Stable Disease	21 (70%)	2 (6.9%)
Progressive Disease	7 (23%)	8 (27.6%)
Disease Control Rate	76.6%	80.8%
Overall Response	6.7%	65%

Table 4: UMCC 2011.53 Response Rates

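### Section 13.3 lets accrual continue after the primary test can no longer succeed; closing accrual at the 14th failure would leave alpha and power unchanged

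*Combined protocol and SAP*

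**What the plan says.** Section 13.2 sets the design: "We will enroll 37 additional patients for comparison of overall survival", with a null rate taken from the statement that "6 month OS in heavily pretreated patients such as those included in this study is 50" per cent, an alternative of 70%, 80% power, and the test "with a type I error rate of 5" per cent. The test asks whether the proportion alive is "greater than the historical rate of 50% with an upper tailed test of binomial proportion". Sections 13.1 and 14.1 count a patient as a success only if alive at 6 months from the start of treatment, count every other patient as unsuccessful, and treat anyone who took any dose as evaluable.

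On timing, Section 13.2 says "we anticipate accrual of approximately 4 patients every 5 months". On monitoring, Section 13.3 says "we plan no interim analysis for futility with data collected in the expansion cohort B", giving as its reason the activity seen in the earlier trial, UMCC 2011.53. Section 1.2 reports of that trial that "the study was stopped due to futility as the observed rate for patients on axitinib was 27" per cent; the endpoint was 6-month PFS judged by RECIST v1.0. The same section gives its median overall survival as 10.9 months (95% CI 6.4 to 17.8).

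**The concern.** The primary endpoint is binary and read at 6 months, while 37 patients at the planned rate take about 46 months to enrol. Most outcomes are therefore known while accrual is still open. In a poorly performing trial, the number of failures can reach the point at which the primary test cannot succeed well before patient 37 enters. The plan has no rule for that moment. The safety monitoring committee in Section 12.13 reviews safety and data integrity quarterly, and Section 19 allows early termination for scientific reasons, but neither is tied to the primary endpoint. At stake are patients enrolled into a trial whose main question has already been answered in the negative.

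**Working it through.** **Inputs.** N = 37, null 0.50, alternative 0.70, one-sided 5%, 80% power, accrual 4 per 5 months = 0.8 per month, no missing data (all Section 13.2); success and failure as in Sections 13.1 and 14.1.

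**1. The plan's own figure.** Let X be the number alive at 6 months among 37.
- P(X ≥ 23 | 0.50) = 0.0939, too large.
- P(X ≥ 24 | 0.50) = 0.0494, within 5%.
- P(X ≥ 24 | 0.70) = 0.8071.

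The stated 80% power and 5% error are reproduced. The cut-off of 24 follows from Section 13.2, which does not print it.

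**2. When success becomes impossible.** With 14 failures, at most 37 − 14 = 23 patients can be alive, one short of 24. Every course of the trial stopped at that point would have failed the test anyway, so alpha stays 4.94% and power stays 80.7%.

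**3. Patients spared by closing accrual at the 14th failure.** Accrual of 37 takes 37 / 0.8 = 46.25 months. The simulation uses 0.8 patients per month and assumes exponential survival. Failures are taken to be deaths, in line with the plan's expectation of no missing data.

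| True 6-month survival | Failures known at once | Quarterly review, assumed lag up to 3 months |
|---|---|---|
| 50% | 29.75 enrolled on average (saving about 7) | 31.5 to 31.7 (saving about 5) |
| 70% | 36.6 | not needed: even less is lost |

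The lag is an assumption. It is motivated by the survival contacts every three months, plus or minus one month (Table 6, footnote 11, and Section 18).

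**4. An optional earlier rule.** Stop accrual at the 11th failure among the first 23 treated (equivalently, 23 − 11 = 12 or fewer alive). Otherwise continue to 37 with the same cut-off. With X1 out of 23 and X2 out of the remaining 14:

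P(success | p) = Σ from x = 13 to 23 of P(X1 = x | 23, p) × P(X2 ≥ 24 − x | 14, p)

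- p = 0.50: 0.0482 (alpha). p = 0.70: 0.8011 (power).
- Chance of stopping, P(X1 ≤ 12): 0.661 at 0.50 and 0.055 at 0.70.

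The saving at a true 50%, measured against 37 and not on top of step 3, depends on how the rule is run:
- Running count, failures known at once: mean enrolment about 26.5 to 26.8, saving about 10.
- Running count, quarterly review with the same assumed lag: about 28.3, saving about 9.
- One look after patient 23 reaches 6 months, accrual paused: 0.661 × (37 − 23) = 9.3.
- The same look without a pause: 6 × 0.8 = 4.8 more patients enter during the wait, so 0.661 × (37 − 23 − 4.8) = 6.1. Simulations gave about 6 to 7.

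**5. Cost to secondary estimates.** Interval width scales roughly with 1/√n. Ending at 30 instead of 37 widens intervals by √(37/30) = 1.11, about 11%; ending at 32 widens them by √(37/32) = 1.08, about 8%.

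**The case against.** The absence of a futility look is a stated decision with a reason, in a 37-patient single-arm trial, and a single-stage design is a permissible choice. That stands, and it is why the earlier stopping rule is offered only as an option.

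A reader might infer that Section 13.3 contradicts Section 1.2, since it cites activity in a trial that was itself stopped for futility. The documents do not support this. The earlier trial stopped on 6-month PFS by RECIST, which the investigators argue misread drug effect as progression. The present endpoint is overall survival, and the earlier median of 10.9 months has a lower confidence limit of 6.4 months, above the 6-month mark. The reason given remains open to question: there was no control group, 30 of 42 patients were available for efficacy, and the Choi re-reading is described as exploratory. But it is not contradicted.

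A second objection is that stopping early leaves hypothesis 2.2 and the Choi-based secondary objectives with fewer patients. That is correct. It is a real cost, though it falls in a trial whose primary test has already failed. A third is that accrual beyond the 14th failure is not required, because NCCN may end the trial. That is also true, but it leaves the decision to discretion without a defined trigger.

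**Conclusion.** The gap is real and cheap to close. With the derived cut-off of 24 of 37, the primary test is lost at the 14th failure, and the plan has no provision to close accrual then. The rule changes neither alpha nor power. At a true 50% it spares about 7 patients if failures are known at once, and about 5 with quarterly review and the assumed lag. These savings rest on 0.8 patients per month and exponential survival; the cut-off rests on exactly 37 patients being analysed.

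A stronger claim is tempting: that a two-stage rule with the same N spares about 10 patients at no real cost. That saving needs a running count, failures known without delay and a true rate of 50%. Run as a single look without a pause, the rule saves about 6. It also leaves power only 0.1 percentage point above the 80% target and reverses a reasoned choice by the investigators. It is a matter for judgement, not a correction of an error.

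**What to change.** 1. Print the success criterion in Section 13.2: at least 24 of 37 alive at 6 months.
2. Add to Section 13.3 that accrual closes when the 14th treated patient is a failure for the primary endpoint, and that the trial is then reported as not meeting that endpoint. Count all failures as in Sections 13.1 and 14.1 (not alive at 6 months), not deaths alone, so that a patient without a confirmed 6-month status is handled as in the final analysis. The rule governs accrual only; follow-up of enrolled patients continues.
3. Optionally, also stop accrual at the 11th failure among the first 23 treated, worded as a running count.
4. First reconcile Section 7.2 with Sections 13.1 and 14.1. Footnote 2 to the schema makes some early drop-outs non-evaluable for the primary endpoint and replaces them, whereas the statistical sections count anyone dosed. Until this is settled, neither the first 23 nor the 14th failure is well defined. Section 13.2 also mentions enrolling 40 eligible patients; if the number analysed is not 37, the cut-off and the failure counts must be recalculated.
5. State in Section 13.3 that the earlier trial stopped for futility on RECIST-based 6-month PFS, not on overall survival, and why that supports the monitoring chosen.

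The cost is one protocol paragraph, the reconciliation in item 4, and a count of failures brought to the existing quarterly review. Item 2 has no cost in alpha or power, but gives somewhat wider secondary intervals if it triggers. Item 3 lowers power from 80.7% to 80.1%.
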